## 4.6 STUDY IMAGES

The images in the study will be obtained using Mirror Photofile software and a 3D digital photography system for image collection, storage, and analysis. To ensure consistent, reproducible study photos from baseline photographs to the 90-day follow-up photographs, Study Sponsor’s specific photography guidelines (refer to Photography Instruction Book for details) and procedures should be followed. The following photographs should be obtained at each specified study visit, for each imaging system used:

- Screening Vectra 3D photograph
- Baseline Vectra 3D photograph,
- Immediate (30-60 minutes) Post-treatment Vectra 3D photograph
- 90-Day Follow-up Vectra 3D photograph

Subject screening photos must be reviewed by trained assessor to ensure proper subject selection and enrollment eligibility and the subject’s menton must be measured to ensure adequate area for quantitative assessment prior to study enrollment. The subject’s baseline images are considered the pre-treatment comparator images.

## 5. TREATMENT OF SUBJECTS AND FOLLOW-UP

In this study, subjects will receive a single Ultherapy treatment.

### 5.1 STUDY TREATMENT

#### 5.1.1 TRANSDUCERS

Two types of transducers will be used during this study:

1. 4 MHz with a 4.5mm focal depth
2. 7 MHz with a 3.0mm focal depth

TABLE 5.1-1

Transducer	GROUP EL2	GROUP EL3	GROUP EL4	Spacing (mm)	TCP's (#)	Depth (mm)	# of Lines	
	Energy (J)							
DS 4-4.5	0.90	1.00	1		1	17	4.5mm	350
DS 7-3.0	0.30	0.35	0	1	23	3.0mm	310	

The region to be treated and the transducer used must be appropriately selected on the Ulthera® system and thus recorded on the Treatment Parameter System Record.

#### 5.1.2 PRE-TREATMENT MEDICATIONS

[figure not shown]
For this protocol, pre-treatment medication will be administered on-site and restricted to Ibuprofen (600mg) taken at least 60 minutes but not more than two hours prior to study treatment.

#### 5.1.3 SUBJECT PREPARATION FOR TREATMENT

The study investigator will first identify the skin areas to which an Ulthera® treatment is to be performed (**Figure 5.1.3-1**). Treatment schematic is for illustrative purposes only. Treatment records for all regions will be maintained in accordance with this protocol.

CONFIDENTIAL – PROPRIETARY INFORMATION

CONFIDENTIAL – PROPRIETARY INFORMATION  
FIGURE 5.1.3-1 TARGET TREATMENT AREAS

CONFIDENTIAL – PROPRIETARY INFORMATION

#### 5.1.4 TREATMENT

All study treatments will be performed by the study investigator and/or trained clinician.

Ultrasound gel will be applied to the transducer, which will then be placed on the targeted skin surface, and ultrasound image will be obtained. Each area of the proposed treatment will be imaged first with the ultrasound device to ensure coupling between the transducer and skin. During the treatment procedure, the study treatment clinician will place multiple Ultherapy® treatment lines close to each other (2 to 3mm) in the selected area, with each treatment line requiring about 3 seconds. Treatment lines can be a maximum length of 25mm and will produce a series of thermal coagulative zones.

Treatment lines to the area highlighted in (**Figure 5.1.3-1**) will be administered as specified by Treatment Group in Section 4.5. These energy settings should not be altered for any study treatments. The first transducer to be used in treatment is the 4-4.5mm, followed by the 7-3.0mm. All study treatments will begin with the 4.5mm depth. The entire 4.5mm depth treatment will be completed prior to continuing to the 3.0mm depth treatment. Treatment will be delivered in a lined pattern. The subject will be monitored during the treatment.

#### 5.1.5 ACUTE RESPONSES

For all exposures, acute responses (e.g., erythema or edema) will be observed by the study treatment clinician and photographically recorded within 30-60 minutes after exposure. If any Serious Adverse Events (SAE) are noted, an SAE Form should be completed.

### 5.2 SAFETY VARIABLES

Prior to treatment, the subject's medical history will be reviewed, a urine pregnancy test will be performed (if applicable), and a physical examination will be conducted. During Ultherapy® treatment, the subject's pain levels will be monitored using a validated Numeric Rating Scale (**Attachment E**). Average pain scores should be obtained following each region treated and for each transducer used during treatment. The average pain score for the entire region treated by each transducer will be recorded. At each subsequent visit, the subject will be queried about adverse events and changes in concomitant medications, and the treatment area will be visually examined. A second pregnancy screening test will be performed at the 90-day follow-up visit.

### 5.3 OUTCOME MEASURES

Quantitative submental lift measurements calculated as detailed in **Attachment A**, comparing improvement in overall lift, will be obtained based on Vectra 3D study images obtained at 90-day follow-up visit post-treatment compared to baseline. The quantitative scale used in the US Pivotal study was designed to measure a quantitative lift however; it was based on Caucasian anatomy. It measured the 2D submental/neck area using 5 quadrants from the menton/neck transition point back toward the neck. In Asian patients the distance from the menton/neck back towards the neck is not as long[6]. Therefore the 5th quadrant was dropped from the measure to account for this anatomical difference. This study will observe the amount quantitative lift by treatment group in this Chinese population.

The Global Aesthetic Improvement Scale (GAIS) (**Attachments B and C**) is a 5-point scale that rates global aesthetic improvement from the pretreatment appearance. The ratings are much worse, worse, no change, improved, and much improved. In this study both live observation and photo review are utilized by the physician (PGAIS) and subject (SGAIS) in order to assign a score. The PGAIS must be performed by the principal investigator. Both the PGAIS and SGAIS should be completed based on a live assessment of the subject while referring to the subject's

CONFIDENTIAL – PROPRIETARY INFORMATION

pre-treatment photographs on a sponsor-supplied electronic tablet (subjects should be given a hand mirror for assessment).

Comparison of improvement data for overall lifting and tightening of skin as determined by a masked, qualitative assessment of photographs obtained at follow-up visits post-treatment compared to baseline as detailed in **Attachment F**.

A validated Numeric Rating Scale (0-10) (**Attachment E**) will be used to record subject reported pain scores during study treatment and following treatment completion. Scores will be obtained for each region treated, for each transducer used, and for the overall treatment.

A Patient Satisfaction Questionnaire (PSQ) (**Attachment D**) will be completed at the 90-day follow-up visit. The subject should complete this assessment while referring to baseline photos on a sponsor-supplied electronic tablet and using a hand mirror.

### 5.3.1 PRIMARY ENDPOINT

The primary endpoint is an assessment of the mean change (improvement) in overall lifting and tightening of skin in Chinese subjects at 90-days compared to baseline in each of the treatment groups as determined by a modified version of the validated quantitative measure of tissue lift in neck/submentum using photographs taken with Mirror Photofile software and a Vectra 3D digital imaging system.

### 5.3.2 SECONDARY ENDPOINTS

The secondary endpoints of this clinical study include for each treatment group:

1. Improvement in overall lifting and tightening of skin as determined by subject response rate (improved or much improved) on Physician Global Aesthetic Improvement Scale (PGAIS) as determined by live assessment compared to baseline photograph.
2. Improvement in overall lifting and tightening of skin as determined by subject response rate (improved or much improved) on Subject Global Aesthetic Improvement Scale (SGAIS) as determined by live assessment compared to baseline photograph.
3. Improvement in overall lifting and tightening of skin as determined by a masked, qualitative assessment of photographs at 90 days post-treatment compared to baseline.
4. Subject satisfaction and subject reported improvement at 90 days post-treatment.

## 5.4 FOLLOW-UP

Subjects will be asked to return to the clinic for follow-up visits at 90 days post-treatment. At all visits, subjects will be assessed for safety and efficacy, standardized images will be taken (refer to study sponsor's study specific photography guidelines and procedures document), adverse events and protocol deviations will be assessed, and study outcome measures (GAIS, other study-specific assessments) will be completed.

At the 90-day follow-up appointment in addition to the above referenced assessments, the subject will complete a Patient Satisfaction Questionnaire and a pregnancy test, if applicable.

Subjects will be asked to return to the site for repeat image if 90-day follow-up image shows photography issues such as lighting inconsistencies, subject positioning, and/or shadowing as determined by photography consultant review.

CONFIDENTIAL – PROPRIETARY INFORMATION

## 5.5 PROTOCOL DEVIATIONS

This study should be conducted as described in this protocol, except for an emergency situation in which the protection, safety, and well-being of a subject requires a protocol deviation, based on the judgment of the investigator (or a responsible, appropriately trained professional designated by the investigator). If the deviation from the protocol is necessary to protect the physical well-being of a subject in an emergency, such protocol deviations must be reported to the Sponsor and the reviewing IRB as soon as possible, but no later than five working days after the emergency occurred.

In the event of a significant deviation from the protocol due to an accident or mistake, the investigator or designee must contact the Sponsor at the earliest possible time by telephone to discuss the deviation and its impact on the study and subject continuation in the study. These discussions will be documented by the investigator and the Sponsor, and reviewed by the monitor.

## 5.6 WITHDRAWAL CRITERIA AND PROCEDURES

All subjects have the right to withdraw at any point during the study without prejudice. The investigator can discontinue any subject, at any time, if medically necessary. The reason for subject's withdrawal should be documented on the appropriate study-specific data form. The subject must undergo the recommended follow-up assessments specified for the last study visit unless contraindicated due to a medical condition. Withdrawn subjects will not be replaced.

## 5.7 END OF STUDY (COMPLETION)

All subjects who have signed an Informed Consent Form, except for screen failures, will be considered enrolled in the study. Subjects who were treated and complete the study duration will be considered to have completed the study. Any subject who does not return for a scheduled follow-up visit will be contacted at least twice by telephone to determine the cause for the missed visit and to try to get the subject scheduled for the follow-up. A new visit will be scheduled as soon as possible. All subjects should be followed until completing the study follow-up or until study discontinuation (withdrawal) for other reasons. The reason for study discontinuation should be documented for each subject. Subjects will be deemed "Lost-to-Follow-up" if they have not returned within two weeks after the last follow-up target. For any subject lost to follow-up at least three attempts to contact the subject must be documented; the attempts must be two phone calls/emails and a registered letter.

# 6. STATISTICAL ANALYSES

For primary and secondary endpoints, data will be summarized for each time point for which data for that parameter are available. Subjects with incomplete data will be included in summaries for which they have data available. Categorical variables will be summarized as frequencies and percentages in each category. Continuous and ordinal variables will be summarized as numbers of subjects, means, standard deviations, medians, and ranges. Graphical presentation of data will be provided, if deemed appropriate. All programs for data output and analyses will be written in SAS® version 9.4 or higher (SAS Institute, Inc., Cary, NC).

## 6.1 EFFICACY ANALYSIS

The primary analysis of efficacy will be based on the evaluable treated subjects, hence, only those subjects who received a complete or partial study treatment and completed the follow-up visit, and who have evaluable images

CONFIDENTIAL – PROPRIETARY INFORMATION

at baseline and 90-days post-treatment will be included in the analysis. No imputations will be performed for missing data.

The primary efficacy endpoint is the amount of improvement from baseline at 90 days after treatment. Descriptive statistics will compare mean values of improvement between the 3 treatment groups and 95% confidence intervals (CIs) will be calculated for each group. Additionally, the proportion of subjects achieving various levels of improvement may be calculated along with exact 95% CIs.

Any deviations from this statistical analysis plan will be documented with justification in the final report.

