Statistical Analysis:	
Descriptive statistics will be used to compare the submental lift, secondary endpoints and safety assessments between the 3 treatment groups at day 90 in this observational trial.

Study Hypothesis:	
The hypothesis for this study is improvement in overall lifting and tightening of skin from baseline to 90 days post-treatment. For each treatment group (energy level), the measure of pre and Day 90 post treatment area of the chin and neck will determine the amount of tissue lift.

Study Duration:	
Estimated timeline: Up to 12 months

CONFIDENTIAL – PROPRIETARY INFORMATION

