## 2. STUDY OBJECTIVE AND DESIGN

### 2.1 STUDY OBJECTIVE

Assess improvement in overall lifting of submental (under the chin) and neck tissue as determined by a quantitative measure of tissue lift in the area using photographs taken with Mirror Photofile software and a Vectra 3D digital imaging system in each of the treatment groups in Chinese subjects.

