### 2.2 STUDY DESIGN

This study is an open-label, non-randomized clinical study to be conducted at up to seven clinical sites. Approximately 60 subjects (20 subjects per treatment group) who meet the eligibility criteria will be enrolled and treated with the Ulthera® System. Enrollment eligibility will be determined by the physician and trained assessors' review and approval of screening images.

Eligible subjects enrolled in the study will be treated using the Ulthera® System by the study investigator and/or trained clinician. Standardized images will be taken at screening, baseline (prior to treatment) and following treatment (30 to 60 minutes post-treatment) and at the 90-day post treatment visit using Mirror Photofile software and a Vectra 3D digital imaging system.

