#### 4.5 SUBJECT TREATMENT GROUP ASSIGNMENT

Subjects are not randomized in this study. All subjects will receive an Ultherapy™ treatment at dual depth using the 4-4.5mm and 7-3.0mm transducers. Treatments will be provided to the lower face, submental (under the chin) and neck area. See Section 5.1 for Study Treatment details. Enrolled subjects will be assigned to one of 3 treatment groups:

Group EL2: Subjects will receive an Ultherapy™ treatment at energy level 2 (EL2).

Group EL3: Subjects will receive an Ultherapy™ treatment at energy level 3 (EL3).

Group EL4: Subjects will receive an Ultherapy™ treatment at energy level 4 (EL4).

Twenty subjects will be enrolled in each group. Enrollment from the original protocol was in the following order: EL3, EL4 and EL2. This amendment (dated 26JAN2018) is to change the order of enrollment. Following amendment approval, approximately 20 patients will be enrolled in EL2, EL3 and EL4 respectively. Enrollment will continue at an energy level until that treatment group is complete.

CONFIDENTIAL – PROPRIETARY INFORMATION

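### Should section 6.1 plan a confidence interval for the difference in mean lift between energy levels, and not only one for each group?

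*Protocol*

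**What the plan says.** Two places in the protocol announce a comparison between groups. Section 6.1, on the primary endpoint, states: "Descriptive statistics will compare mean values of improvement between the 3 treatment groups and 95% confidence intervals (CIs) will be calculated for each group". The statistical paragraph of the synopsis states: "Descriptive statistics will be used to compare the submental lift, secondary endpoints and safety assessments between the 3 treatment groups at day 90", and calls the study observational.

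The statements of purpose are all within group. Section 2.1 sets the objective as lift measured with the "Vectra 3D digital imaging system in each of the treatment groups in Chinese subjects". Section 5.3.1 defines the endpoint as the "mean change (improvement) in overall lifting and tightening of skin in Chinese subjects at 90-days compared to baseline in each of the treatment groups". Section 5.3 adds: "This study will observe the amount quantitative lift by treatment group in this Chinese population". The synopsis hypothesis is improvement from baseline to day 90, measured separately at each energy level.

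On reporting, section 6 says: "Continuous and ordinal variables will be summarized as numbers of subjects, means, standard deviations, medians, and ranges". The only other intervals in the protocol are optional exact ones for proportions reaching given levels of improvement (section 6.1). On design, section 2.2 says: "This study is an open-label, non-randomized clinical study to be conducted at up to seven clinical sites", and section 4.5 says: "Enrollment will continue at an energy level until that treatment group is complete".

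The supplied SAP covers only the masked photograph assessment. Its Introduction leaves all other endpoints, including quantitative lift, to a separate SAP that is not among the documents.

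**The concern.** The verb in section 6.1 is to compare, and the natural uncertainty measure for a comparison is an interval for the difference. The protocol plans an interval for each mean and none for EL3−EL2, EL4−EL2 or EL4−EL3. A reader left with three means and three intervals may judge by whether the intervals overlap, and overlap is a much stricter standard than a 95% interval for the difference. Such a reader could see two overlapping intervals and conclude that the energy levels do not differ when the interval for the difference would exclude zero. What would be at stake is the reading of the energy-level contrast. The within-group estimates of lift would be unaffected.

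**Working it through.** The documents state no power, SD, effect size or sample-size derivation, so there is no figure of the plan's own to reproduce. Everything below is in units of the SD of lift, with equal SDs assumed unless stated.

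**Inputs.** 20 subjects per group (sections 2.2 and 4.5). Confidence level 95% (section 6.1).

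**1. Planned interval for one group mean.** Half-width = t(0.975, n−1)/√n = 2.093/√20 = 0.468.

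**2. Unplanned interval for a difference of two means.** Half-width = t(0.975, 2n−2)·√(2/n) = 2.024·√0.1 = 0.640.

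**3. Separation of two group intervals.** This requires a difference above 2 × 0.468 = 0.936. The ratio is 0.936/0.640 = 1.46. As a two-sample test, t = 0.936/√0.1 = 2.96 on 38 df, p = 0.005. Overlap is therefore a poor stand-in for an interval on the difference.

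**4. Sensitivity to unequal SDs (assumed values).** Without assuming equal variances:

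| SDs in the two groups | Half-width of difference | Group intervals separate beyond | Ratio |
|---|---|---|---|
| 1 and 1 | 0.640 | 0.936 | 1.46 |
| 1 and 1.5 | 0.820 | 1.170 | 1.43 |
| 1 and 2 | 1.024 | 1.404 | 1.37 |

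The arithmetic behind the concern is correct. The ratio is, however, a general property of two intervals at this sample size. It says nothing particular about this plan.

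**5. Is information missing?** No. For groups i and j the unadjusted interval is (mean_i − mean_j) ± t·√(SD_i²/n_i + SD_j²/n_j), with Welch degrees of freedom computed from the same SDs and n. Every term is among the statistics that section 6 commits to report. Only a display is absent.

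**6. Does anything depend on the difference?** Sections 2.1, 5.3 and 5.3.1 and the synopsis hypothesis all refer to each group's own change from baseline. The interval in step 1 is the interval for that quantity. No documented success criterion, choice of energy level or stopping rule uses a pairwise contrast. Setting n, mean, SD, median, range and a 95% interval side by side for three groups is a descriptive comparison, which is what section 6.1 and the synopsis announce.

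**7. Would the added intervals be a clear gain?** The groups are not randomised and are filled in sequence, so a difference in means mixes energy level with enrolment period. The table gives the chance of each signal at 20 per group with equal SDs, by simulation, for an assumed true difference in means from whatever cause:

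| Difference in means (SD) | Interval for difference excludes zero | Group intervals separate |
|---|---|---|
| 0.3 | 15% | 3% |
| 0.5 | 34% | 10% |
| 0.8 | 69% | about 36% |
| 1.0 | 87% | 59% |

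The same rows apply if the whole shift comes from enrolment period and none from energy. The greater sensitivity detects confounding as readily as effect. Under no difference at all, at least one of three unadjusted intervals excludes zero in about 12% of trials.

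**The case for a change.** The strongest case for acting is that the protocol itself chose to compare the groups, so it should show how uncertain the comparison is. An interval for the difference does that directly and needs no new data. It would guard against reading overlap as equality, and its width would also discourage ranking three point estimates as if they were precise. Fixing the method in advance, without assuming equal variances, spares each reader from improvising. A label saying descriptive, unadjusted and not causal would carry the caution about the design.

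Much of this stands. The gap between 0.640 and 0.936 is real, the protocol plans no such interval, and adding one would be legitimate and cheap.

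It does not show a fault. The harm needs a reader who applies an overlap rule that appears nowhere in the documents. The interval can be had from the planned summaries, and no conclusion the study sets out to draw would change. A label does not alter what the interval responds to: in sequentially filled groups it would flag a period shift more often, and readers would be inclined to take it as a dose response. A statistician could reasonably leave it out for that reason. What is shown is also only the protocol's silence, because the SAP that governs this endpoint has not been seen.

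**Conclusion.** The concern does not hold. The interval planned in section 6.1 matches the estimand, which is mean change in lift within each energy level, and following the section as written gives sound results for the stated objective. The descriptive comparison it announces is met by the side-by-side summaries. The 46% discrepancy between overlap and a difference interval (0.936 against 0.640 SD at 20 per group) is correctly computed but affects only an assumed way of reading the results. It changes no planned estimate, precision, bias or decision. Intervals for pairwise differences would be an optional display with a real trade-off in a non-randomised, sequentially enrolled pilot.

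The SD-unit figures assume 20 evaluable subjects per group and, except where unequal SDs are shown, equal SDs. The conclusion itself does not depend on those values. It rests on the within-group purpose, the absence of any decision tied to a contrast, and the reporting of n, mean and SD by group. It would need another look only if the separate SAP for this endpoint attached a formal conclusion to differences between energy levels.
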